6.7. Frequency of visits and follow up period

Participants will be assessed at baseline, regular 4-weekly intervals throughout the 24-week trial (weeks 4, 8, 12, 16, 20, 24), and at a post-discontinuation follow-up 4 weeks after completion of the trial as outlined in Table 1. Interviews with participants will take an average of 40-60 minutes. If participants cannot be seen face-to-face due to safety concerns, interviews will be conducted via online platforms such as Zoom, Skype or over teleconference as a last resort. Once enrolled, participants will be reimbursed for travel up to the value of \$20, per visit, or to cover internet expenses. Visits must occur within one week of the pre-determined date (based on baseline visit date). If a visit occurs more than 7 days after the pre-determined date, this will be a deviation from protocol. If participants cannot attend any visit before 2 weeks from the pre-determined date, this visit will be skipped until the next scheduled assessment. A skipped visit will also be a deviation from protocol.

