4.4. Efficacy Variables

The primary outcome variable will be the MADRS total score at the end of the 24-week treatment phase.

Secondary outcomes include the Bipolar Depression Rating Scale (BDRS), Young Mania Rating Scale (YMRS) and Hamilton Anxiety Rating Scale (HAM-A) scores. Participant life satisfaction will be rated on the self-reporting scale (Q-LES-Q). Functioning measures will include the Social and Occupational Functioning Assessment Scale (SOFAS), and Longitudinal Interval Follow-Up Evaluation-Range of Impaired Functioning Tool (LIFE-RIFT). The Clinical Global Impressions Bipolar Version (CGI-BP) will be used to rate clinician judgement for improvement and severity of illness. The Patient Global Impression Scale (PGI) will be used to rate participant perception. We will ask participants to complete a number of pen and paper based cognitive tasks; digit span forwards and backwards, trail making and the Symbol Digit task.

In order to undertake a cost-utility analysis (CUA), gains in utility for the participants will be measured in the study. The most common metric developed to measure utility gains from health interventions is the QALY. A QALY is simply calculated by multiplying the period of time spent in a particular health state by the "utility" or preference value assigned to that health state measured on a scale from 0 (denoting death) to 1 (denoting full health). There are different techniques of deriving utility however the simplest is via the use of a multi-attribute utility instrument which is basically a health related quality of life measure (HRQoL) which has pre-determined "weights" assigned to the health states included within the measure – this is called indirect elicitation of utility. We propose to use the AQol4D to assess any utility based HRQoL gains. It comprises four separately scored dimensions, consisting of independent living, relationships, mental health, and senses. It consists of 12 items and takes 2 minutes to complete. The main utility algorithm of the AQoL has been scored using the time trade off method and the questionnaire has sound psychometric properties. The AQoL4D will be administered to study participants at baseline, 12 and 24 weeks. Scoring will be completed with the algorithm provided by the developers of the instrument obtained from: http://www.aqol.com.au/scoring-algorithms.html .

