6.4. Screening assessment

No study specific procedures or investigations will be performed before the participant has signed and dated the informed consent form. After consent has been obtained, a research assistant will conduct the screening assessment as per Table 1. This will include a full assessment of all inclusion and exclusion criteria. In the event that face-to-face recruitment is not possible due to safety concerns, we will alter recruitment to utilise online methods including Zoom, Skype, or teleconference as a last resort. If screening via an online method, participants will not be asked to provide blood specimens. Participants will be provided with the PICF either in hard copy or electronically, as they prefer. Once received, the participants will have the opportunity to review the information and discuss with anyone they deem relevant. The researcher will review the PICF document over the telephone or via an online medium with the participant and establish consent. Participants either will be able to sign the PICF and return electronically or will be provided with a reply paid envelope to mail hardcopy documents back to the researcher for sighting and archiving. If the participant does not meet one of the requisite inclusion criteria, they will not take further part in the trial. For example, if the initial assessment reveals that a participant does not actually meet a diagnosis of bipolar disorder I or II, or bipolar disorder not elsewhere classified (NEC), or that their MADRS score is lower than 20, or they do not meet current major depressive episode on the SCID-5-RV, then they will be withdrawn based on the fact that they do meet inclusion criteria. These participants will be deemed to be 'screen fails' and will be constituted as such in the CONSORT flowchart.

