6.10. Doses and treatment regimens

Trial medication will be dispensed on a monthly basis, so there will be a total of six dispensations per participant. The medication will be provided to the participant after the baseline visit has been completed and the participant has been randomised. The trial medications will be supplied by the site pharmacy. Participants will be instructed to return all containers to allow capsule counts by the trial monitor and the trial pharmacist. In the event that face-to-face visits are unable to be conducted due to safety concerns, medications will either be delivered to participants front doors or mailed directly to participants. Participants will be provided with reply paid envelopes to post remaining medication back to the researcher.

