9.2. Method of statistical analysis

All analyses will be conducted in accordance with the International Conference on Harmonization E9 statistical principles, and are based on all randomised participants with at least one post-baseline observation (intention to treat population). Reporting of research findings will be done in accordance to CONSORT guidelines. The statistician responsible for the analysis of outcome data will be blind to group allocation. The primary efficacy analysis will assess average treatment group differences for the primary outcome measure MADRS total score over the entire study period and will use a likelihood based mixed-effects model, repeated measures approach (MMRM). The MMRM model includes the fixed, categorical effects of treatment, investigator, visit, and treatment-by-visit interaction, as well as the continuous, fixed covariates of baseline score and baseline score-by-visit interaction. The MMRM includes all available data at each time point and is the preferred method of analyzing clinical trial data in psychiatry as compared to more traditional repeated measures analysis of variance (ANOVA) and analysis of covariance models (ANCOVA). Planned comparisons will be done with the MMRM models to determine between group differences in change of symptoms measures from baseline to week 24. Results from the analysis of dichotomous data will be presented as proportions, with 95% confidence interval, and Fisher's exact p-value where appropriate. Non-parametric statistics will be used when assumptions for parametric methods are violated. Effect sizes will be calculated using Cohen's guidelines. All tests of treatment effects will be conducted using a two-sided alpha level of 0.05 and 95% confidence intervals. Change scores in symptoms and in biological markers will be derived. Pearson Product Moment Correlations will be used to examine the relationships between the change scores for symptoms and the change scores for biological markers in the two groups. Using Fisher's z transformation, we will test whether the correlations obtained for each group are statistically different in terms of strength.

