9.3. Sample size and power

We are aiming for a target sample size of 150 participants. For a two tailed analysis with α =0.05, $Z\alpha$ = 1.96 and with β =0.2, $Z\beta$ = 0.8, N=120, the study should be powered at 80% to detect a true difference in MADRS scale score between the mangosteen pericarp and placebo groups if the effect size is

Cohen's *d*=0.362 or greater. This is a conservative estimate, based on the results of the pilot data. However, in our previous trial of N-acetylcysteine specifically investigating bipolar depression, effect sizes for depressive symptoms (BDRS, MADRS), clinical global impression of depressive severity (CGI BP-depression), as well as all functional measures have shown effects similar to or above the effect size the sample has been calculated for. Based on our previous trials we typically have an attrition rate of 20%. Therefore, although power calculations indicated 120 participants will be sufficient to detect between group differences, we plan to recruit 150 participants to account for attrition.

10.Ethics

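### Safety concerns are the only stated trigger for a remote interview, and a visit not attended within two weeks is skipped with no remote attempt, so obtainable MADRS ratings can be lost, most seriously at week 24

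*Protocol*

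**What the plan says.** Section 6.7 schedules assessments every four weeks from baseline to week 24, with a follow-up at week 28. On remote contact it says: "If participants cannot be seen face-to-face due to safety concerns, interviews will be conducted via online platforms", with teleconference as the last option. Two other provisions carry the same condition:

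- Section 6.4, on screening: "In the event that face-to-face recruitment is not possible due to safety concerns, we will alter recruitment to utilise online methods".
- Section 6.10, on delivery and return of medication: "In the event that face-to-face visits are unable to be conducted due to safety concerns".

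On missed visits, section 6.7 says: "If participants cannot attend any visit before 2 weeks from the pre-determined date, this visit will be skipped until the next scheduled assessment", and then "A skipped visit will also be a deviation from protocol". A visit more than 7 days late but inside the two weeks still takes place, as a deviation.

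Table 1 has the MADRS rated at every visit. Section 4.4 states: "The primary outcome variable will be the MADRS total score at the end of the 24-week treatment phase". Section 9.2 analyses it by MMRM and notes: "The MMRM includes all available data at each time point".

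**The concern.** The remote route has a narrow stated trigger, while the skip rule applies whatever the reason for non-attendance. A participant who has moved away, is in hospital elsewhere, or is too depressed to travel for more than two weeks past the due date meets the skip rule but not clearly the remote rule. The visit then yields no MADRS, although the protocol accepts remote interviews elsewhere, including the screening at which the MADRS decides eligibility.

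At weeks 4 to 20 the next on-treatment visit follows in four weeks. At week 24 it does not: the next scheduled assessment is week 28, after treatment has stopped, and cannot stand in for the primary time point.

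The reason for not attending may be related to current mood. The MMRM allows for that only as far as the participant's observed scores predict the missing one.

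**Working it through.** **1. The text.** Remote contact appears in three places.

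| Provision | Section | Stated condition |
|---|---|---|
| Remote screening, including the MADRS eligibility rating | 6.4 | safety concerns |
| Remote follow-up interview | 6.7 | safety concerns |
| Remote medication supply and return | 6.10 | safety concerns |
| Skipped visit | 6.7 | not attended within two weeks, any reason; no remote attempt required |

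No section offers a remote interview for another reason, and none expressly rules it out.

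**2. The plan's own allowance for loss.** Section 9.3 says: "Based on our previous trials we typically have an attrition rate of 20" per cent. 120 / (1 − 0.20) = 150, so the recruitment target reproduces, and 120 completers are 60 per arm. Section 9.3 does not say whether attrition counts only participants who leave the trial or also those who stay but have no week-24 rating.

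**3. Size, under stated assumptions.** The documents give no rate of non-attendance by reason. Assume that a fraction f = 5% to 15% of week-24 ratings is lost, that every one could have been obtained remotely, and that week 20 is observed and correlates with week 24 at ρ = 0.6 to 0.8. None of these values comes from the protocol.

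- With no borrowing from earlier visits, the SE is multiplied by √(1 / (1 − f)).
- With borrowing from week 20, the SE is multiplied by √(1 + [f / (1 − f)] × (1 − ρ²)).

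Lower end: 1 + (0.05 / 0.95) × (1 − 0.64) = 1.019, and the square root is 1.009.
Upper end: 1 + (0.15 / 0.85) × (1 − 0.36) = 1.113, and the square root is 1.055.

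| f | SE rise, no borrowing | ρ = 0.6 | ρ = 0.8 |
|---|---|---|---|
| 5% | 2.6% | 1.7% | 0.9% |
| 10% | 5.4% | 3.5% | 2.0% |
| 15% | 8.5% | 5.5% | 3.1% |

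The two right-hand columns are the relevant ones, since the plan uses an MMRM. Their range is about 1% to 5.5%. If week 20 is also missing, the figure moves towards the no-borrowing column; if further visits add information, it falls.

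**4. In terms of power.** Take any effect that would have 80% power without the loss (two-sided 5%, normal approximation). Its expected z-value is 1.960 + 0.842 = 2.802.

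- SE up 0.9%: 2.802 / 1.009 = 2.777; 2.777 − 1.960 = 0.817; power about 79%.
- SE up 5.5%: 2.802 / 1.055 = 2.656; 2.656 − 1.960 = 0.696; power about 76%.

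These figures concern the week-24 comparison. Section 9.2 also describes a group difference over the whole study period, in which a single lost visit weighs less.

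**The case against.** **The text does not prohibit.** Section 6.7 says when remote interviews will be held, not that they are barred otherwise. Neither safety concerns nor attendance is defined, and reimbursement for internet costs suggests that an online contact counts as a visit. A site could treat a participant too ill to travel as a safety case. This stands: a reader might infer that the protocol forbids remote interviews for other reasons, and it does not. But the wording leaves the sites free to read it differently, and none is told to try remotely before skipping.

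**The skip is not immediate.** A reader might infer that anyone who cannot come in on the day loses the visit. Section 6.7 allows two weeks, and short illness, work or caring duties will often resolve in that time. This also stands, and it limits the point to absences that outlast the window.

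**Face-to-face rating is a reasonable default.** The same condition in three sections looks deliberate, and one mode for a rated primary outcome has merit. That supports preferring in-person visits. It does not support having no rating rather than a remote one, when the protocol accepts a remote rating in other circumstances.

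**The harm is built on assumptions.** This stands in large part. The 5% to 15% has no source in the documents, some participants would be unreachable remotely too, and the loss may overlap with the 20% already planned for. A reader might also infer a bias in a known direction. The documents do not support that: those who stay away could be the more unwell or the more recovered, and nothing suggests different skip rates by arm in a blinded trial.

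**Conclusion.** The point holds in a limited form. Following section 6.7 as written can lose MADRS ratings that an accepted route could have obtained, with the greatest consequence at week 24. It is an avoidable gap in data collection, not a contradiction or an error in a stated figure.

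The size cannot be derived from the documents. The SE increase of about 1% to 5.5% under the MMRM is conditional on the assumed loss, full recoverability and the assumed correlations. It should not simply be added to the 20% attrition: if those missed ratings are already counted there, wider remote access would reduce the planned loss rather than prevent an additional one. No bias figure is warranted. The label is a cheap improvement.

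**What to change.** In section 6.7, keep face-to-face as the default and state three things:

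- If a participant cannot attend in person within the visit window, for any reason, a remote interview is attempted, by video first and then by telephone.
- The visit is skipped only if neither an in-person nor a remote interview is possible.
- The mode (in person, video, telephone) is recorded at each visit, so that a sensitivity analysis can account for it.

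Section 6.10 ties remote medication supply to the same safety condition, and Table 1 makes the visits at weeks 4 to 20 dispensing visits. A change to 6.7 alone would leave the two sections out of step, so they must be reconciled. Blood sampling and the pen-and-paper cognitive tasks need no change.

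The cost is a minor protocol amendment with ethics review and one additional eCRF field. The remote route and the reimbursement of internet expenses already exist. The downside is a somewhat larger share of MADRS ratings made remotely, a mixture the protocol already permits and which the recorded mode would make it possible to examine.

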4.6. Withdrawal Criteria

Withdrawal from the trial will occur if the participants cease taking their trial medication for seven consecutive days or if the participants cease effective contraception or becomes pregnant or if the participant commences new Electroconvulsive Therapy (ECT) treatment. Dose changes to existing medications (either increases or decreases in dose), or addition or removal of an agent will be accepted and participants will be allowed to continue with the trial. Participants will be withdrawn from the study if they withdraw consent or at the discretion of the researcher given adverse events or loss to follow-up. Serious adverse events will not require automatic withdrawal from the study.

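### The skip rule in section 6.7 makes no exception for week 24, so an obtainable primary MADRS may go uncollected; for weeks 4 to 20 it is not reconciled with supply and withdrawal

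*Protocol*

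**What the plan says.** **Visit timing (Protocol 6.7).** Assessments fall at baseline, every four weeks to week 24, and "at a post-discontinuation follow-up 4 weeks after completion of the trial as outlined in Table 1". The window is set by "Visits must occur within one week of the pre-determined date (based on baseline visit date". Lateness beyond that is tolerated for a time: "If a visit occurs more than 7 days after the pre-determined date, this will be a deviation from protocol". Beyond two weeks the visit is not held: "If participants cannot attend any visit before 2 weeks from the pre-determined date, this visit will be skipped until the next scheduled assessment". The section classes this, too, as a deviation. Video or telephone interviews are provided for, but only where face-to-face contact is ruled out by safety concerns.

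**Primary time point (4.4 and Table 1).** "The primary outcome variable will be the MADRS total score at the end of the 24-week treatment phase". Table 1 marks week 24 as the primary endpoint visit and week 28 as follow-up after discontinuation.

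**Analysis (9.2).** The primary mixed model estimates "average treatment group differences for the primary outcome measure MADRS total score over the entire study period" and uses all available data at each visit. The change from baseline to week 24 is a planned comparison within it.

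**Supply (6.10 and Table 1).** "Trial medication will be dispensed on a monthly basis, so there will be a total of six dispensations per participant". Table 1 marks dispensing at visits 1 to 6 (weeks 0 to 20). Delivery or mailing is described only for safety concerns. Capsules per pack, any spare supply, and resupply after a skipped visit are not stated.

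**Withdrawal (4.6 and 6.8).** Under 4.6, participants are withdrawn if they "cease taking their trial medication for seven consecutive days". Under 6.8, the trigger is more than seven days off trial medication.

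**The concern.** One rule covers two different situations. Skipping an interim visit loses one of several repeated measures. Skipping week 24 loses the measurement that 4.4 names as the primary outcome, and no later on-treatment visit can stand in for it. Site staff who follow 6.7 as written would not take a MADRS from a participant who can first be seen, or first be telephoned, 15 days after the due date. A score that is never collected cannot be recovered at analysis; a late one can at least be examined.

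For weeks 4 to 20 there is a second question. If capsules are handed out only at visits, a skipped visit also means a missed dispensation. Section 6.7 expects that participant back at the next assessment, while 4.6 and 6.8 may already have withdrawn them. Sites could then handle identical cases differently, and read literally, withdrawal from the trial would end later MADRS collection as well.

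**Working it through.** The protocol gives no figure for late attendance or for its effect, so there is none to reproduce. The check is calendar arithmetic plus an illustration of size.

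**1. Calendar.** Visits fall every 28 days from baseline (6.7, Table 1):
- week 20 = day 140 (last dispensing visit)
- week 24 = day 168
- skip limit for week 24 = 168 + 14 = day 182
- week 28 = day 196

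**2. Time off drug around week 24.** Assume full adherence and no capsules carried over from earlier packs. With a pack of *p* days, supply ends on day 140 + *p*: day 168 for *p* = 28 and day 171 for *p* = 31.
- At week 28: 196 − 168 = 28 days off drug, or 196 − 171 = 25 days.
- At a permitted week-24 visit 8 to 14 days late (days 176 to 182): 8 to 14 days off drug with 28-day packs, 5 to 11 with 31-day packs. The two-week limit therefore does not guarantee on-drug measurement.
- At a contact after the limit but before week 28 (days 183 to 195): between 183 − 171 = 12 and 195 − 168 = 27 days off drug.

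**3. Interim visits, weeks 4 to 20.** Assume the previous visit was on time, adherence is full, and there is no resupply outside visits. Pack size is an assumed range of 28 to 42 days.
- Gap when a visit is *L* days late = 28 + *L* − *p*.
- Gap when one visit is skipped = 56 − *p*.

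| Pack (days) | 7 days late | 14 days late | One visit skipped |
|---|---|---|---|
| 28 | 7 | 14 | 28 |
| 31 | 4 | 11 | 25 |
| 35 | 0 | 7 | 21 |
| 42 | none | 0 | 14 |

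A skipped visit exceeds seven days at every pack size in the range. To stay clear of the 4.6 trigger, 56 − *p* must be below 7, so *p* must be at least 50 days; for 6.8 it must be at least 49. Neither fits monthly dispensing easily. A visit that is late but held is less clear-cut: 14 days late gives 14, 11, 7 or 0 days without supply, depending on the pack.

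The two withdrawal wordings differ at a gap of exactly seven days, which triggers 4.6 but not 6.8. With 28-day packs that gap arises at a visit seven days late, which is still inside the 6.7 window.

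**4. Size at week 24 (assumed rates).** Section 9.3 plans 150 recruited with 20% attrition: 150 × 0.8 = 120. If a further share *s* of those 120 lacked week 24, a simple comparison of observed week-24 scores would have its standard error multiplied by 1/√(1 − *s*).

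| Assumed *s* | Scores missing (120 × *s*) | Standard error multiplied by |
|---|---|---|
| 2% | 2.4 | 1.01 |
| 5% | 6 | 1.03 |
| 10% | 12 | 1.05 |

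These are upper figures for the loss of precision at those rates. The mixed model draws on up to five earlier post-baseline scores per participant, and some late attenders may already be counted in the 20%.

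**The case against.** **Nothing is thrown away.** A reader might infer that the plan discards primary data. It does not: the visit is not held, so the value is missing. The window already runs from about a week before to two weeks after the due date, and only participants outside it are affected. This stands, and the point is non-collection.

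**A very late score is not the week-24 outcome.** On monthly packs it is 12 to 27 days off drug, and the third hypothesis in 3.1.3 treats the post-discontinuation period as a separate question. Declining to label such a score as week 24 is defensible. This also stands, and it shapes the fix. It does not justify leaving the score uncollected, nor does it explain why telephone or video is closed to a participant who could be reached within the limit.

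**The model limits the damage.** Earlier visits are retained, and the primary contrast in 9.2 averages over the study period. A reader might infer a material loss of power; the protocol gives no rate of late attendance to support that, and the illustration above is small.

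**The supply clash is an inference.** It depends on pack size and resupply, which may be set out in pharmacy documents, and missed doses would leave capsules in hand. It does not arise at week 24, where nothing is dispensed. It is fair to say that the sections do not fit together on a plain reading. It would be too strong to say that they contradict each other outright, or that late attendance as such becomes withdrawal.

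**Who attends late.** It is tempting to say that the missing scores would come mostly from people who are unwell. The protocol says nothing on this, so it is not relied on here.

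**Conclusion.** The concern holds in a limited form. As written, 6.7 lets the primary time point be skipped like any interim visit. The only later assessment is at week 28, about 25 to 28 days after supply ends on packs of 31 to 28 days. The result is avoidable missing data at week 24. It bears mainly on the outcome defined in 4.4 and on the planned week-24 comparison, and less on the averaged contrast in 9.2. Its size cannot be stated: at assumed rates of 2 to 10% of 120, the standard error of a simple week-24 comparison would rise by about 1 to 5%. The case for change is that the loss is preventable at low cost, not that it is shown to be large.

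The supply and withdrawal question is secondary and conditional. If capsules are supplied only at visits and taken in full, one skipped visit at weeks 4 to 20 leaves 14 to 28 days without supply for packs of 42 to 28 days, beyond the triggers in both 4.6 and 6.8. The one-day difference between those two triggers is in the text itself and depends on no assumption.

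**What to change.** Amend 6.7 so that:
- the week-24 MADRS is exempt from the skip rule;
- telephone or video may be used for that visit whenever attendance in person is not possible, not only for safety concerns, with the existing two-week limit as the target;
- if the limit is still missed, the MADRS is taken at the earliest contact before week 28, recording the date and whether trial medication was still being taken.

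State in advance how these scores are used. Those within the existing limit enter the primary model as week 24. Later ones are flagged, kept out of the week-24 value in the primary model, and included in a prespecified sensitivity analysis. The week-28 assessment stays separate.

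Reconcile 4.6, 6.7, 6.8 and 6.10 on what happens to supply and trial status when an interim visit is late or skipped, and align the two withdrawal wordings. No position is taken on what the clinical rule should be.

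The cost is a short amendment, two extra recorded items, and a few remote or late assessments.
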